3. INVESTIGATIONAL PLAN

3.1 Overall Study Design and Plan

This is a multicenter, single-arm, open-label, single- and multiple-dose study to assess the safety, tolerability, and PK of cefiderocol in hospitalized paediatric subjects 3 months to < 18 years of age with a suspected or confirmed aerobic Gram-negative bacterial infection (including but not limited to cUTI, cIAI, HAP/VAP, and sepsis or BSI) caused by a suspected or confirmed aerobic Gram-negative pathogen requiring systemic antibiotics for an expected 5 to 14 days.

The study will consist of 4 separate cohorts of paediatric subjects grouped according to age range ([Table 3-1](#)).

Table 3-1 Cohort Description

Cohort	Age Range	Single-dose Phase (minimum per cohort)	Multiple-dose Phase (minimum per cohort)
1 ^a	12 to < 18 yrs	N = 6	Cohort 1 not applicable in multiple-dose phase
2 ^{a,b}	6 to < 12 yrs	N = 6	N = 10
3 ^{a,b}	2 to < 6 yrs	N = 6	N = 10
4 ^c	3 mos to < 2 yrs	N = 6	N = 10

mos = months; PK = pharmacokinetic; yrs = years

- a Cohorts 1, 2, and 3 single-dose phase will be initiated in parallel.
- b The multiple-dose phase (Cohorts 2, 3, and 4) will begin after safety and PK data from 6 subjects in the corresponding single-dose cohort have been assessed.
- c Cohort 4 (single dose) will begin after safety and PK data from at least 6 subjects from single-dose Cohorts 1, 2, and 3 (with a minimum of 3 subjects from Cohort 3) have been assessed.

The single-dose phase (in all 4 cohorts) will enroll subjects with Gram-negative bacterial infection and will confirm cefiderocol exposures in a minimum of 6 subjects prior to conducting a multiple-dose phase (in Cohorts 2, 3, and 4) in additional subjects.

Cohort 1 will consist of a single-dose phase only.

Cohorts 2, 3, and 4 will each consist of both a single-dose phase and a multiple-dose phase (an expected 5 to 14 days). Note: a minimum of 6 doses will be permissible if, in the opinion of the investigator, it is in the subject's best interest.

The single-dose phase of Cohorts 1, 2, and 3 will be initiated in parallel. Within the single-dose Cohorts 2, 3, and 4, the PK of cefiderocol will be determined in all subjects prior to initiating enrollment of subjects in the multiple-dose phase of each respective cohort.

Single-dose Cohort 4 (the youngest age group) will begin after safety and PK data is evaluated from a minimum of 6 subjects from the single-dose Cohorts 1, 2, and 3 (with a

minimum of 3 subjects from Cohort 3). Multiple-dose cohorts will begin after analyzing safety and PK data from 6 subjects in the corresponding single-dose cohort.

Enrollment will be stopped for the applicable cohort to allow for analysis of the PK data prior to moving from single-dose to multiple-dose in Cohorts 2, 3, and 4. Sites that are activated for enrollment will be instructed via email or a phone call from the sponsor or clinical research organization (CRO) to pause enrollment in the relevant age cohort, until the available data have been processed and evaluated; additionally, interactive response technology (IRT) will be de-activated to prevent enrollment until data have been evaluated. The phone call will be followed by written notification via “Dear [name]”.

In the single-dose phase, each of the 4 cohorts will include a minimum of 6 paediatric subjects (at least 24 subjects total).

In the multiple-dose phase (Cohorts 2, 3, and 4), each cohort will include a minimum of 10 paediatric subjects (at least 30 subjects total).

Overall, it is expected that at least 54 evaluable paediatric subjects will be enrolled in the study across all 4 cohorts.

For summary of plasma cefiderocol concentrations, evaluable subjects in the single-dose phase will include those who have received 1 dose of cefiderocol and who have at least 1 PK blood sample above the limit of quantification. In the multiple-dose phase, evaluable subjects will include those who have received ≥ 4 doses of cefiderocol and who have at least 1 PK blood sample above the limit of quantification.

Screening will occur within 4 days prior to Treatment Day 1 or on Treatment Day 1 in both the single- and multiple-dose phase. Prior to Screening, sites will be asked to send a Permission to Screen Form to Shionogi’s medical monitor for evaluation and agreement. The purpose of the form is to check the eligibility of potential subjects being enrolled into the study.

[figure not shown]
In the single-dose phase, cefiderocol will be administered (in addition to SOC) at any time during the SOC treatment regimen. In the multiple-dose phase, cefiderocol will be administered on Day 1 (in addition to SOC), within 72 hours of the start of potentially effective treatment with SOC antibiotics for infection. Subjects will subsequently receive cefiderocol every 8 hours (q8h) for an expected 5 to 14 days; the total duration of cefiderocol administration will be determined by the investigator based on clinical assessment of each subject’s infection status. Each dose of cefiderocol will be administered IV over 3 hours. The infusion may be shortened if this is in the best interest of the subject and if approved by the sponsor via the Request for Shortened Infusion Duration Form. The single-dose phase will include only those subjects with normal renal function or mild renal impairment. The dose of cefiderocol for the single-dose phase will be determined based on body weight only; the maximum dose to be administered is not to exceed 2000 mg. The dose for the multiple-dose phase will be determined based on both body weight and renal function; the maximum dose to be administered is not to exceed 2000 mg. The SOC administered will be selected by the investigator based on the

suspected or confirmed pathogen(s) for the infection in accordance with local standards and can be modified at any time during the subject's participation in the study at the investigator's discretion. In the multiple-dose phase, if the subject's infection is confirmed to be Gram negative only before starting treatment, monotherapy with cefiderocol may be allowed.

End-of-treatment (EOT) assessments will occur within 24 hours after administration of cefiderocol (single-dose phase) or within 24 hours after administration of the last dose of study treatment (multiple-dose phase), or at early termination. A further clinical assessment will occur at a Posttreatment visit 7 (\pm 4) days after EOT (multiple-dose phase), which is analogous to a TOC and EOS time point, if microbiological samples are available. The EOS visit will occur 28 (+ 7) days after administration of cefiderocol in the single-dose phase or 28 (+ 7) days after administration of the last dose of study treatment in the multiple-dose phase; this visit may be performed on-site or via phone call. The study schematic including a schedule of assessments is provided in [Figure 3-1](#) and [Table 3-2](#).

The total duration of cefiderocol administration will be determined by the investigator based on clinical assessment of each subject's infection status but should be expected (at time of enrollment) to be 5 to 14 days. Note: a minimum of 6 doses will be permissible if, in the opinion of the investigator, it is in the subject's best interest. In special circumstances, treatment beyond 14 days may be allowed following review and approval of individual cases by the Shionogi medical monitor via the Treatment Extension Form. The dose of cefiderocol administered to each subject will be determined by the investigator based on dosing recommendations ([Section 5.2](#)).

Figure 3-1 Study Schematic

PK = pharmacokinetic

Cohort 1 is not applicable in the multiple-dose phase.

Multiple-dose Cohorts 2, 3, and 4 will begin after PK analyses are complete.

Table 3-2 Study Schedule of Assessments

Study Phase	Screening	Cefiderocol Administration	End-of-Treatment (EOT)	Post-treatment Visit	End-of-Study (EOS) Visit
Single-dose	Within 4 days prior to Treatment Day 1 or on Treatment Day 1	1 day	Within 24 hours after last dose of study treatment (or early termination)	NA	28 (+ 7) days after single dose of cefiderocol
Multiple-dose		5 to 14 days		7 (\pm 4) days after EOT	28 (+ 7) days after last dose of study treatment

NA = not applicable

Safety assessments including physical examinations, vital sign measurements, and clinical laboratory tests will be performed at prespecified time points during Screening, during study treatment, and after administration of study treatment within 24 hours. In addition, safety data will be captured at various time points during the study from safety assessments performed as part of routine patient care ([Section 7.5](#)). Adverse events will be collected and monitored from the time signed informed consent/assent is obtained through the end of study (EOS) visit or 28 (+ 7) days after administration of cefiderocol in the single-dose phase or 28 (+ 7) days after administration of the last dose of study treatment in the multiple-dose phase.

Blood samples for determination of plasma cefiderocol concentrations will be collected from each subject at prespecified time points during and/or after the cefiderocol infusion ([Section 7.4](#)). Cefiderocol PK will be determined in the single-dose phase in each of the cohorts; cefiderocol dose recommendations may be revised by the sponsor prior to initiating enrollment of subjects in the multiple-dose phase of each respective cohort.

In the multiple-dose phase only, clinical outcome data and microbiological outcome data will be obtained. Clinical and microbiological outcome assessments will be performed at EOT, at the Posttreatment visit (7 \pm 4 days after EOT), and EOS if available. Data from assessments performed prior to, during, and after treatment with SOC antibiotics as part of routine patient care will be captured as study data. The time points for collection of microbiological specimens are otherwise not prespecified by the protocol (Posttreatment Visit, EOT, and EOS, if available; [Section 7.6](#)). In subjects where it is not possible to obtain a posttreatment culture and/or EOS culture, determination of presumed microbiological eradication may be made based on resolution of all presenting clinical sign and symptoms of the infection (clinical cure).

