Clinical Outcome: Clinical outcome assessments (signs and/or symptoms of infection eg, fever, irritability, pain, physical signs such as increased heart rate) will be performed at EOT (within 24 hours of administration of the last dose of study treatment or early termination), and at a Posttreatment visit 7 (\pm 4) days after EOT (multiple-dose phase) and at EOS (conducted on site or as a phone call). Additionally, any available clinical outcome data used for the initial diagnosis of infection and obtained at any time after initiation of study treatment (cefiderocol alone or administration with SOC) as part of routine patient care will be captured as study data.

Microbiological Outcome: If available, microbiological data (Gram stain, culture, colony forming units, or sensitivity results, and pathogen identification) for specimens collected at the initial diagnosis of infection and obtained at any time after initiation of study treatment as part of routine patient care will be captured as study data and used to assess microbiological outcome. The time points for collection of microbiological specimens are otherwise not prespecified by the protocol (EOT, Posttreatment Visit, and EOS, if applicable). In subjects where it is not possible to obtain a posttreatment culture and/or EOS culture, determination of presumed microbiological eradication may be made based on resolution of all presenting clinical sign and symptoms of the infection (clinical cure).

Statistical Methods:

Unless otherwise noted, continuous variables will be summarized by using the number of nonmissing observations (N), arithmetic mean (mean), standard deviation (SD), median, minimum, and maximum values as summary statistics; categorical variables will be summarized by using the frequency count and the percentage of subjects in each category as summary statistics.

For summary of plasma cefiderocol concentrations, evaluable subjects in the single-dose phase will include those who have received 1 dose of cefiderocol and who have at least 1 PK blood sample above the limit of quantification. In the multiple-dose phase, evaluable subjects will include those who have received \geq 4 doses of cefiderocol and who have at least 1 PK blood sample above the limit of quantification.

No inferential statistical testing will be performed in this study.

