7.6.1.1.1 HAP/VAP/cIAI

- **Clinical Cure:** Resolution or substantial improvement of baseline signs and symptoms of pneumonia/cIAI.
- **Clinical Failure:** No apparent response to therapy; persistence or worsening of baseline signs and/or symptoms of pneumonia/cIAI; reappearance of signs and/or symptoms of pneumonia/cIAI; development of new signs and/or symptoms of pneumonia/cIAI requiring antibiotic therapy other than, or in addition to, study treatment therapy; progression of chest radiographic abnormalities; or death due to pneumonia/cIAI.
- **Indeterminate:** Lost to follow-up such that a determination of clinical cure/failure cannot be made.

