7.6.1.1.2 Complicated Urinary Tract Infection

- **Clinical Cure:** Resolution or substantial improvement of baseline signs and symptoms of cUTI, or return to preinfection baseline if known, such that no antibiotic therapy is required for the treatment of the current infection.
- **Clinical Failure:** No apparent response to therapy; persistence or worsening of baseline signs and/or symptoms of cUTI; or reappearance of signs and/or symptoms of cUTI; development of new signs and/or symptoms of cUTI requiring antibiotic therapy other than, or in addition to, study treatment therapy; or death due to cUTI.
- **Indeterminate:** Lost to follow-up such that a determination of clinical cure/failure cannot be made.

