7.6.1.1.3 BSI/Sepsis

- **Clinical Cure:** Resolution or substantial improvement of baseline signs and symptoms. Subjects with bacteremia must have eradication of bacteremia caused by the Gram-negative pathogen.
- **Clinical Failure:** No apparent response to therapy; persistence or worsening of baseline signs and/or symptoms, reappearance of signs and/or symptoms; development of new signs and/or symptoms requiring antibiotic therapy other than, or in addition to, study treatment therapy; or death due to BSI/sepsis.
- **Indeterminate:** Lost to follow-up such that a determination of clinical cure/failure cannot be made.

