7.6.2.1.1 HAP/VAP/cIAI and BSI/Sepsis

- **Eradication:** Absence of the baseline Gram-negative pathogen from an appropriate clinical specimen. If it is not possible to obtain an appropriate clinical culture and the subject has a successful clinical outcome, the response will be presumed to be eradication.
- **Persistence:** Continued presence of the baseline Gram-negative pathogen from an appropriate clinical specimen.
- **Indeterminate:** No culture obtained from an appropriate clinical specimen or additional antibiotic therapy for the treatment of the current infection including missed sampling.

7.6.2.1.2 cUTI

- **Eradication:** A urine culture shows the baseline Gram-negative uropathogen found at entry at $\geq 10^5$ colony forming units (CFU)/mL are reduced to $< 10^3$ CFU/mL.
- **Persistence:** A urine culture shows that the baseline Gram-negative uropathogen found at entry at $\geq 10^5$ CFU/mL grows $\geq 10^3$ CFU/mL.

- **Indeterminate:** No urine culture obtained or additional antibiotic therapy for the treatment of the current infection including missed sampling.

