- j Multiple doses of cefiderocol administered as an IV infusion over 3 hours, q8h, beginning on Day 1 and continuing for an expected 5 to 14 days. Note: Shorter infusion times may be allowed in the multiple-dose phase if agreed on by the sponsor and in the best interest of the subject via the Request for Shortened Infusion Duration Form. In special circumstances, treatment beyond 14 days may be allowed following review and approval of individual cases by the Shionogi medical monitor via the Treatment Extension Form.
- k Cohort 2: Blood samples will be collected once at each time point: at 1, 3 (within 15 minutes prior to the end of infusion using a separate line or immediately after the end of infusion using the same line and with proper flushing), 3.5, 5, and 8 hours after the start of infusion for the single dose and Cohort 2 for the multiple dose phase during one of the dosing intervals from the 6th to the 12th dose of cefiderocol. Pharmacokinetic sampling schedule is shown in [Table 7-2](#).
- l Cohorts 3 and 4: Blood samples will be collected once at each time point at 3 (within 15 minutes prior to the end of infusion using a separate line or immediately after the end of infusion using the same line and with proper flushing), 5, and 8 hours after the start of infusion for the single dose and during one of the dosing intervals from the 6th to the 12th dose of cefiderocol during the multiple dose phase. Pharmacokinetic sampling schedule is shown in [Table 7-2](#).
- m Clinical outcome assessments will be performed at EOT, Posttreatment, and EOS if available; additional clinical outcome assessments may be performed as part of routine patient care.

-
- n Microbiological specimens may be collected as part of routine patient care and time points are not otherwise prespecified per protocol (EOT, Posttreatment Visit, and EOS, if applicable). In subjects where it is not possible to obtain a posttreatment culture and/or EOS culture, determination of presumed microbiological eradication maybe made based resolution of all presenting clinical sign and symptoms of the infection (clinical cure).

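### Presumed microbiological eradication has two incompatible triggers in the protocol, and the SAP's per-subject rule drops the condition that no culture could be obtained

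*Protocol*

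**What the plan says.** **Overview passages.** Protocol Section 3.1 covers children for whom a post-treatment or end-of-study culture cannot be obtained. Eradication may then be presumed "based on resolution of all presenting clinical sign and symptoms of the infection (clinical cure"). The Synopsis (Microbiological Outcome) has the same sentence. Appendix 1 footnote n repeats it with small typing errors: "maybe made based resolution of all presenting clinical sign and symptoms of the infection (clinical cure"). None of the three makes an exception by infection type.

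**Clinical cure.** The outcome definitions are broader:
- HAP/VAP/cIAI (Protocol 7.6.1.1.1): "Resolution or substantial improvement of baseline signs and symptoms of pneumonia/cIAI".
- cUTI (7.6.1.1.2): "Resolution or substantial improvement of baseline signs and symptoms of cUTI, or return to preinfection baseline if known", such that antibiotics are no longer needed.
- BSI/sepsis (7.6.1.1.3): "Resolution or substantial improvement of baseline signs and symptoms. Subjects with bacteremia must have eradication of bacteremia caused by the Gram-negative pathogen".

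SAP Section 8 carries the same definitions.

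**Microbiological outcome.** For infections other than cUTI, Protocol 7.6.2.1.1 says that where a culture cannot be obtained and "the subject has a successful clinical outcome, the response will be presumed to be eradication". SAP Section 8 repeats that sentence. For cUTI, Protocol 7.6.2.1.2 and SAP Section 8 make a missing urine culture Indeterminate and offer no presumption.

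**SAP additions.** SAP Section 8 contains two things that Protocol 7.6.2.1.1 does not. A missed sample is Indeterminate only if the reason was something other than clinical success. In the per-subject rule, a child with an infection other than cUTI who is a clinical cure at the visit counts as eradicated; that sentence does not require a culture to have been unobtainable.

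**Scoring and reporting.** The investigator determines the outcome and enters it in the eCRF (Protocol 7.6.2.1, SAP Section 8). Indeterminate stays in the denominator as nonresponse (SAP 6.4.2). SAP Section 12 declares no change from the protocol's planned analyses.

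**The concern.** One reported category, Eradication, has two entry conditions, and no passage says which governs. Because investigators make the entry, sites working from the overview or the schedule footnote can classify the same child differently from sites working from Section 7.6. The recorded categories are Eradication, Persistence and Indeterminate. None separates documented from presumed eradication, and no microbiological table title in SAP Section 15 indicates that split, so the difference would not be visible in the planned tables.

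Presumption may be common. After treatment starts, specimens are taken where possible and if clinically indicated (Protocol 7.5.3.2), and the sampling times are otherwise not prespecified (Section 3.1). The reported eradication rate may therefore depend heavily on the presumption rule. Microbiological response is the secondary objective for cefiderocol alone and exploratory otherwise.

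**Working it through.** No stated figure bears on this point, so the check sets the rules side by side for each type of child.

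| Child | Synopsis, 3.1, App. 1 note n | Protocol 7.6.2.1 | SAP 8, per subject |
|---|---|---|---|
| A. Non-cUTI, non-bacteremic, all signs resolved, no culture obtainable | May be presumed eradicated | Eradication | Eradication |
| B. As A, but improved with residual signs | Basis not met: Indeterminate | Eradication | Eradication |
| C. cUTI, all signs resolved, no urine culture | May be presumed eradicated | Indeterminate | Indeterminate |
| D. cUTI, improved only, no urine culture | Basis not met: Indeterminate | Indeterminate | Indeterminate |
| E. Non-cUTI, clinical cure, culture obtained and still positive | Not addressed (a culture exists) | Persistence | Eradicated by the cure sentence; Persistence by the next rule |

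Rows A and D agree. Rows B and C conflict within the protocol. Row E is a conflict inside the SAP if its cure sentence is read literally, because no order of precedence is given.

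Bacteremic children are left out of row B. Their definition of cure already requires eradication of the bacteremia, so substantial improvement alone does not lead to presumed eradication.

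**Size.** Let n be the MITT denominator of a table cell, and let b, c and e be the numbers of children in rows B, C and E.
- Eradication rate under Protocol 7.6.2.1 minus the rate under the overview passages (if every permitted presumption is made) = 100 × (b − c)/n points.
- Further change from the SAP per-subject sentence read literally = up to +100 × e/n points.

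Rows B and C pull in opposite directions, so the net sign is not known in advance. For one type of discordance, with k children:

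| n | k = 1 | k = 2 | k = 3 |
|---|---|---|---|
| 10 | 10.0 | 20.0 | 30.0 |
| 30 | 3.3 | 6.7 | 10.0 |

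The values 10 and 30 are the planned minimum per multiple-dose cohort and for the three cohorts together (Protocol 3.1). They serve only as examples of n. The analysis denominator is MITT, which requires a baseline Gram-negative pathogen, and its size is not given. If a monotherapy MITT cell held 5 children (an assumed size), one child would move the rate by 100 × 1/5 = 20 points.

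**The case against.** The strongest reply is that the tables have one rule. The overview sentences are permissive (presumption may be made), and Section 3.1 points to Section 7.6, which states the mandatory rule. The SAP's presumption sentence matches Protocol 7.6.2.1.1. Efficacy assessment is described as deliberately not rigorous (Protocol 7.7), there is no inferential testing, and sample size ignores efficacy.

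Much of this stands. It rules out three stronger readings that a reader might infer:
- *That clinical outcome is also scored differently by section.* It is not. Cure has one operative definition per infection type, repeated in the SAP. The stricter phrase appears only within the presumption sentence, with cure as a parenthetical label.
- *That the SAP adopted a looser threshold than the protocol while declaring no change.* On the threshold, it follows Protocol 7.6.2.1.1. Its departures are the missing culture condition per subject and the added qualifier on missed sampling.
- *That the shift can be estimated.* One could suppose that 20 of 30 children are cured without a culture and that 20% to 40% of them are improved only. That gives 4 to 8 children, or 4/30 = 13 to 8/30 = 27 points. The documents support neither assumption, 30 is not the MITT size, and cUTI and bacteremic children must be removed.

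The reply does not remove the conflict. Reading Section 7.6 as governing is reasonable, but no passage says so, and the schedule footnote is a working instruction to sites. It also leaves the cUTI mismatch and the SAP per-subject sentence untouched.

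**Conclusion.** The inconsistency is real and confined to microbiological outcome. It affects three groups: improved-only, non-cUTI, non-bacteremic children without a culture; fully resolved cUTI children without a culture; and, on a literal reading of the SAP, non-cUTI clinical cures whose culture remains positive. Each discordant child moves the eradication rate by 100/n points. The total is unknown because the documents give neither the MITT size nor the number of such children.

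The primary safety and PK objectives, the sample size and the clinical outcome summaries are unaffected. The point is worth correcting because cells are small and the tables as indexed would not show how much of the rate is presumed. The documents do not settle which threshold should apply; they require that there be only one.

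**What to change.** 1. Reconcile the Synopsis, Section 3.1, Appendix 1 footnote n, Section 7.6.2.1 and SAP Section 8 to a single presumed-eradication rule.
2. State in that rule whether it applies to cUTI.
3. Align the parenthetical clinical-cure label in the three overview passages with the definitions in 7.6.1.1, or remove it.
4. Restore in the SAP per-subject rule the condition that a culture could not be obtained, so that clinical cure does not override an available culture. If any departure from the protocol is kept, record it with its reason in SAP Section 12, as Protocol 9.1 requires.
5. Show documented and presumed eradication as separate rows in the microbiological outcome tables (14.2.1.4.1 to 14.2.1.6).

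The cost is minor wording changes in both documents and one extra table row. The split also requires each Eradication entry to be traceable to a culture or to its absence.
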